2.3.4 Sensitivity Analyses to Evaluate Possible Impact of COVID-19

In order to evaluate the possible impact of COVID-19 on the primary and secondary endpoints, sensitivity analyses will be implemented. A COVID-19 subject is defined as any subject obtaining a positive COVID-19 test either prior to enrollment or during the 12-month follow-up or having an adjudicated COVID-19 related or possibly related adverse event during the 12-month follow-up. The following analyses will be included:

Statistical Analysis Plan

- 1) The primary endpoint will be analyzed excluding COVID-19 subjects from the denominator for the calculation of the composite success rate.
- 2) The primary endpoint will be analyzed excluding primary endpoint adverse events adjudicated as related or possibly related to COVID-19.
- 3) A subgroup analysis will be performed to examine the consistency of results for the primary endpoint between COVID-19 subjects and non-COVID-19 subjects.
- 4) All secondary endpoints will be evaluated excluding adverse events adjudicated as related or possibly related to COVID-19.

Other sensitivity analyses recommended based on available guidelines and modalities related to COVID-19 may also be performed as appropriate.

2.4 Interim Analysis

No formal interim analysis is planned for this study to stop the trial early due to futility or success.

2.5 Timing of Analysis

The primary endpoint analysis will be performed, and the clinical report prepared when all randomized subjects have reached a primary endpoint and the study has been unblinded.

2.6 Study/Trial Success

The trial will be considered successful if null hypothesis of the primary endpoint is rejected (i.e. the placebo group is non-inferior to the aspirin group).

2.7 Handling of Missing Data

[REDACTED]

[REDACTED]

2.8 Multiplicity Issues

This study includes a single primary endpoint. Thus, no Type I error adjustment is necessary.

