2.2 Hypothesis

Withdrawal of antiplatelet therapy from the antithrombotic regimen of HM3 pump patients will not adversely affect safety or efficacy of the HM3 and may reduce non-surgical bleeding.

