3.0 CLINICAL INVESTIGATION DESIGN

This is a prospective, randomized, double-blinded, placebo-controlled clinical investigation of advanced heart failure patients treated with the HM3 with two different antithrombotic regimens: vitamin K antagonist with aspirin versus vitamin K antagonist with placebo. Subjects will be randomized in a 1:1 ratio.

Clinical Investigation Plan

The clinical investigation has been designed to involve as little pain, discomfort, fear, and any other foreseeable risk as possible for subjects. Refer to the Risks Analysis section of the clinical investigation plan for details.

The clinical investigation will be conducted at up to 50 centers worldwide. Greater than 50% of the patients enrolled in this study will be from centers based in the United States. The primary and secondary endpoints will be evaluated according to the statistical section (Section 8 and in the study statistical analysis plan; SAP). Outcomes for this study include death, transplant, withdrawal or pump exchange. All subjects, site, Clinical Events Committee (CEC), and sponsor personnel will remain blinded to the randomization scheme until the last ongoing study subject completes follow-up (specifically, experiences an outcome or has final study visit) and all data have been collected and adjudicated. Exceptions will be justified in the study blinding plan (e.g. DSMB). After a patient reaches 12-months of follow up, they will continue to be followed every 6-months, as long as they remain on the treatment arm medication, until the last ongoing patient reaches 12-months of follow up. Beginning at the 12-month follow-up visit, patients should be requisitioned two bottles of the treatment arm medication to cover the 6 months until the next follow up visit.

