5.7 Number of Subjects

This study will enroll enough subjects to randomize 628 subjects in the clinical investigation. No site may randomize more than 15% of the total number of randomized subjects without Sponsor authorization.

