Primary Endpoint Evaluation	The primary endpoint composite success rate will be calculated for each treatment arm based on the number of subjects who survive to 12 months with no primary endpoint events divided by the total number of subjects in the Modified Intention to Treat Population (mITT) population. The placebo arm will be considered non-inferior to the aspirin arm if the lower boundary of the one-sided 97.5% confidence limit of the risk difference in the composite success between treatment arms (Placebo-arm minus Aspirin-arm) is greater than the non-inferiority margin (10%).
Number of Subjects Required for Inclusion in Clinical Investigation	[REDACTED]
Secondary Endpoint	
• Non-surgical Major Hemorrhagic Events• Non-surgical Major Thrombotic Events• Survival• Stroke Rates,• Pump Thrombosis Rates• Bleeding Rates, including:
○ Non-surgical Bleeding○ Moderate Bleeding○ Severe Bleeding○ Fatal Bleeding○ GI Bleeding
Descriptive Endpoints	Hemocompatibility Score, Rehospitalizations, Economic Cost Implications

Clinical Investigation Plan

Subject Follow-up	
- Baseline- Implant- Randomization- Discharge- Week 1 ± 3 days- Month 1 ± 7 days- Month 3 ± 30 days- Month 6 ± 30 days- Month 9 ± 30 days- Month 12 ± 30 days- Every 6 month ± 60 days until last subject has completed the 12-month follow-up.
Inclusion Criteria	
• Subject will receive the HeartMate 3 per standard of care (SOC) in accordance with the approved indications for use in the country of implant.• Subject will receive the HeartMate 3 as their first durable VAD.• Subject must provide written informed consent prior to any clinical investigation related procedure.• In patients of child bearing capability, not currently pregnant and on appropriate contraception.

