2.3.2 Secondary Endpoints

The secondary endpoints will be analyzed using the mITT population.

Non-surgical Major Hemorrhagic events: Hemorrhagic event rate per patient year will be calculated by dividing all non-surgical bleeding events and hemorrhagic stroke events by the cumulative years of study exposure. This rate will be compared between groups using Poisson regression.

Non-surgical Major Thrombotic events: The thrombotic event rate per patient year will be calculated by dividing the number of non-surgical ischemic strokes, pump thrombosis and arterial peripheral thromboembolic events by the cumulative years of study exposure. This rate will be compared between groups using Poisson regression.

Survival: The overall survival rate will be analyzed using a Kaplan-Meier analysis and the treatment groups compared using the log-rank test. Survival will be calculated starting at 14 days post implant.

Stroke Rate: The stroke rate will be calculated based on the number of strokes experienced by subjects, 14 days or more after device implant, and while on their treatment assignment, divided by the cumulative duration of study exposure (years of support). The treatment groups will be compared by using Poisson regression.

All strokes that occur 14 or more days after implant will be included, regardless of the treatment status of the subject (subjects who move off their randomized treatment will continue to be followed). Ischemic and hemorrhagic stroke rates and debilitating stroke rate (MRS > 3) will also be analyzed. The stroke rate and treatment comparison will be performed as described above.

Time to first non-surgical stroke event will also be analyzed using a Kaplan-Meier analysis. The treatment groups will be compared using a log-rank test.

Statistical Analysis Plan

Pump Thrombosis: The pump thrombosis rate will be calculated based on the number of suspected or confirmed pump thrombosis events experienced by the subject, 14 or more days post device implant, while on their treatment assignment divided by the cumulative duration of study exposure (years of support). The treatment groups will be compared by using Poisson regression.

All suspected pump thrombosis that occurs 14 or more days post implant will be included, regardless of the treatment status of the subject (subjects who move off their randomized treatment will continue to be followed). The pump thrombosis rate and treatment comparison will be performed as described above.

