Bleeding: All bleeding events that occur will be captured. Subjects who terminate the study prematurely without experiencing any bleeding will have the time they were in the study counted in the analysis. For the mITT population, bleeding events will be included while the subject remains on their randomization assignment until the last randomized patient has been followed to one year. This will result in some subjects being followed for more than one year.

Bleeding rates will be differentiated based on severity and will include moderate bleeding, severe bleeding and fatal bleeding. Gastrointestinal (GI) bleeding and non-surgical bleeding will also be analyzed. The bleeding rate (events per patient year) will be calculated by dividing the number of bleeding events by the cumulative duration of study exposure (years of support). Bleeding rates will be compared between treatment groups using Poisson regression. In addition, a subgroup analysis will be performed according to subject aspirin responsive testing.

In addition, all secondary endpoints will be analyzed to include non-surgical major hemocompatibility related adverse events beyond the time of transition to open label in the mITT population.

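### In the unredacted text, SAP 2.8 controls Type I error only for the primary test; six bleeding comparisons have no order, key endpoint or nominal label

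*SAP*

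**What the plan says.** SAP 2.8 is visible in full: "This study includes a single primary endpoint. Thus, no Type I error adjustment is necessary". SAP 2.6 defines trial success as rejection of the primary null hypothesis, that is, non-inferiority of placebo. Protocol Appendix VIII bases that test on the "lower boundary of the one-sided 97.5% confidence limit of the risk difference in the composite success between treatment arms", with a 10% margin. SAP 2.4 plans no formal interim analysis for futility or success.

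The hypothesis in Protocol 2.2 has a second part: withdrawal of antiplatelet therapy will not harm safety or efficacy "and may reduce non-surgical bleeding". Protocol 15.1 and Appendix VIII repeat this, and Protocol 5.4.1 gives fewer bleeds as the possible gain for Medicare beneficiaries.

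SAP 2.3.2 sets out the comparisons that bear on that part. For non-surgical major hemorrhagic events, "This rate will be compared between groups using Poisson regression". For moderate, severe, fatal, GI and non-surgical bleeding, "Bleeding rates will be compared between treatment groups using Poisson regression". A separate hemorrhagic stroke rate is also analysed. The section ends by repeating every secondary endpoint with events after open-label transition. SAP 2.3.4 repeats them again without COVID-19-related events.

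**The concern.** One primary endpoint is a good reason for leaving the primary test unadjusted. It gives no protection to any other claim. The result most likely to be promoted if placebo does well is a reduction in bleeding, and the visible plan does not say which comparison would establish it. Non-surgical bleeding and non-surgical major hemorrhagic events differ only by hemorrhagic stroke, and the hypothesis could be read onto either.

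The secondary endpoints cannot simply be taken as exploratory. Protocol 4.2 and SAP 1.4.2 say that they will be compared between arms, SAP 2.3.2 assigns tests to them, and SAP 1.4.3 keeps a separate descriptive class. Without a named endpoint, a real bleeding benefit would be reported as one nominal p-value among several, open to the charge of selection.

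**Working it through.** **Inputs from the documents.** The primary test uses a one-sided 97.5% limit, so its alpha is 1 − 0.975 = 0.025 one-sided. Protocol 5.7 randomizes 628 subjects, and Protocol 3.0 says "Subjects will be randomized in a 1:1 ratio", so there are 628 / 2 = 314 per arm. The success rate, power and dropout behind 628 are redacted, so that figure cannot be reproduced; here it serves only to set the arm size.

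**Assumption on level.** The visible SAP gives no significance level for secondary tests. I take two-sided 0.05, which is 0.025 in the direction favouring placebo.

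**Counting the tests (SAP 2.3.2).**
- Bleeding comparisons: non-surgical major hemorrhagic, non-surgical, moderate, severe, fatal, GI = 6. With the hemorrhagic stroke rate, 7. With the open-label repeat, 12 to 14.
- Whole secondary list before repeats: hemorrhagic, thrombotic, survival (3); all, ischemic, hemorrhagic and debilitating stroke, and time to first stroke (5); pump thrombosis (1); five bleeding rates (5) = 14.

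**If the tests were independent and the arms did not differ.** The chance of at least one false result favouring placebo is 1 − 0.975^k:
- k = 1: 2.5%
- k = 6: 1 − 0.975^6 = 14.1%
- k = 7: 1 − 0.975^7 = 16.2%
- k = 12: 1 − 0.975^12 = 26.2%

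**Allowing for overlap.** The tests share events, so independence gives upper figures. With six equally correlated normal statistics, the chance of a false result favouring placebo is 12.1%, 10.4%, 8.1% and 5.4% at pairwise correlations of 0.3, 0.5, 0.7 and 0.9.

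A more structural check simulated overlapping Poisson counts with no difference between arms. None of the following rates comes from the documents: 314 patient-years per arm on treatment, 0.3 or 0.5 bleeds per patient-year, severity split 45/50/5% (moderate/severe/fatal), half of bleeds GI, hemorrhagic stroke 0.03 per patient-year, and added open-label time of 10% or 25%.

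| Family | Any false positive, two-sided | Falsely favours placebo |
|---|---|---|
| 6 bleeding tests | 18.9–19.2% | 9.5–9.9% |
| 12 (with open-label repeat) | 23.3–26.2% | 11.8–13.2% |

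**Superiority from the primary interval.** A lower limit above 0 is also above −10 percentage points, so a superiority finding always lies inside a non-inferiority finding. Simulating 314 per arm with assumed aspirin-arm success rates of 0.65 and 0.75 gives false non-inferiority of 2.55% and 2.51% at a true difference of −10 points, and false superiority of 2.52% and 2.53% at a true difference of 0. No alpha is spent by reading both.

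**Cost of the alternatives.** Bonferroni over six bleeding tests needs p < 0.05 / 6 = 0.0083. A fixed sequence needs no split: each step is tested at its full level only if the previous one succeeded, so the one-sided familywise error stays at 0.025, provided that each test holds its own level.

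**The case against.** The best defence is that nothing visible promises a confirmatory bleeding claim. The hypothesis says only that bleeding may fall, SAP 1.4.2 frames the secondary endpoints as an assessment of safety, and success is non-inferiority alone. For the primary test SAP 2.8 is correct: one endpoint, one-sided 0.025, no efficacy interim. All of that stands. It supports labelling the secondary results nominal, but the visible SAP does not label them.

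Two stronger readings are tempting, and the documents do not support them.

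A reader might infer that the bleeding claim rests on 14 tests with a 51% chance of a false positive. The arithmetic is right (1 − 0.95^14 = 51.2%), but 14 is the whole secondary list, including survival, thrombotic events, ischemic stroke and pump thrombosis. The figure is also two-sided and assumes independence.

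A reader might also infer that the plan has no superiority step, so that superiority could not be claimed with a controlled error rate. The first half cannot be shown: SAP 2.3.1.3 and Protocol Section 8, whose contents list includes 8.2.3 Secondary Endpoint Analyses, 8.6 Multiplicity and 8.11 Success Criteria, are redacted. SAP 2.6 defines success without excluding a later superiority test. The second half is wrong: superiority read from the same interval, endpoint and population is already error-controlled. At most there is a pre-specification gap.

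**Conclusion.** The point holds for the bleeding comparisons in the unredacted text. A claim of less bleeding chosen from the six named outcomes carries a false-positive risk of roughly 10% to 14% in the favourable direction, four to six times the 2.5% of one pre-named test. The 14% assumes independence and is an upper figure for six tests; the 10% rests on assumed event rates and overlap. Even at a pairwise correlation of 0.9 the risk is about double (5.4%). Adding the hemorrhagic stroke rate or the open-label repeat raises it further.

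The primary non-inferiority conclusion is unaffected. The change is worth making because it is cheap and decides whether a bleeding result can be confirmatory.

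**What to change.** Rewrite SAP 2.8 as a short fixed sequence, settled before unblinding:

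1. Non-inferiority of the primary composite, as now.
2. One named bleeding endpoint at two-sided 0.05, tested only if non-inferiority is met. An example is the non-surgical major hemorrhagic event rate in the mITT population. State whether events after open-label transition count, and the follow-up window.
3. Superiority of the composite, read from the primary interval (lower limit above 0).

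Steps 2 and 3 may be swapped, but the order must be fixed. If superiority comes first, a composite that also contains death, stroke and thrombosis could block the bleeding test.

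Report all other secondary comparisons, including the open-label and COVID-19 repeats, as estimates with 95% confidence intervals labelled nominal. If SAP 2.3.1.3 or Protocol Section 8 already contains a hierarchy or superiority step, bring SAP 2.6 and 2.8 into line with it instead.

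The sequence deals with multiplicity only. The named bleeding test must hold its own level, so the SAP should also say how its Poisson model allows for repeated bleeds in the same patient.

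The cost is SAP wording, with no patients and no alpha taken from the primary test. The downside is that results outside the sequence cannot be presented as confirmatory.

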2.9 Baseline and Demographic Characteristics

The following baseline characteristics will be descriptively presented according to treatment assignment: demographics, medical history, INTERMACS profile, vital signs, medications, laboratory assessments, coagulation assessments, hemodynamic assessments, and echocardiogram results. Continuous variables will be reported as a mean with standard deviation, and by quartiles, minimum and maximum values. Categorical variables will be reported as the number and percentage of subjects in each category.

Statistical Analysis Plan

2.10 Adverse Events

Adverse events are described in Section 6.8.1 of the ARIES HM3 Clinical Investigational Plan and defined in Appendix II of that document. Adverse events that occur within one year of implant will be reported per randomized treatment group. Adverse events in consented patients who are not reflected in the analysis populations (i.e. not randomized or who experience surgical events - ≤14 days post implant) will be summarized separately from the two treatment arms of the study. The data will be presented as the number and percentage of all subjects enrolled who experience the event and the total number of events.

Adverse events in the analysis populations will be presented as number and percentage of all subjects enrolled who experience the event, the total number of events and the events rate (events per patient year). Adverse events will also be analyzed according to their severity.

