5.8 Total Expected Duration of the Clinical Investigation

The expected duration of each subject's participation is at least 12 months and up to 36 months post-implant. Scheduled visits and data collection for this clinical investigation will occur at Baseline, Implant, Randomization, Week 1 \pm 3 days, Discharge, Month 1 \pm 7 days, Month 3 \pm 30, Month 6 \pm 30 days, Month 9 \pm 30 days, Month 12 \pm 30 days and, in patients still on the treatment arm medication, follow up will continue every 6 months \pm 60 days until the final ongoing patient completes their month 12 follow up visit. Subjects not on the treatment arm medication will be exited from the trial at the conclusion of their month 12 follow-up visit. The expected duration of enrollment is 24 months. Therefore, the total duration of the clinical investigation is expected to be 36 months.

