6.8.1 Continued follow up beyond 12-months post implant

Subjects on the treatment arm medication will be followed every six months after the 12-month follow up visit until the final ongoing subject reaches the 12 month visit or experiences a study outcome. Only treatment arm medication details, subject status (including death, withdrawal, or transplant) along with adverse events and device deficiencies will be collected along with additional supportive data should adverse events or device deficiencies occur. If a patient's clinical course after 12 months of follow up requires transition to open-label, the patient will be considered to have reached the end of study follow up unless the transition to open label is due to a stroke, in which case the patient should be followed for an additional 60-days to capture the MRS score. The clinical reason for transition to open-label will be captured. Subjects transitioned to open label prior to 12 months of follow up should be followed to their 12-month follow up.

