7.3 Adverse Event and Device Deficiency/Device Malfunction Reporting

7.3.1 Adverse Event Reporting

Safety surveillance and reporting starts as soon as the patient is enrolled in the clinical investigation. Adverse events occurring prior to randomization which disqualify a patient for randomization, but occur after consent, will be captured in the EDC and, if necessary, should be reported to the sponsor through standard commercial practices. Safety surveillance and reporting will continue until the last follow-up visit has been performed, the subject is deceased, the subject concludes participation in the clinical investigation or the subject withdraws from the clinical investigation. All adverse event, deaths, and device deficiency data will be collected throughout the time period defined above and will be reported to the Sponsor on a CRF. Additional information about an adverse event should be updated within the appropriate CRF. An offline form will be made available to allow the investigator to report SAEs in the event the entry cannot be made in the EDC. This offline form can be submitted by email to [contact]. This does not replace the EDC reporting system. All information must still be entered in the EDC system as soon as feasible.

Unchanged, chronic, non-worsening or pre-existing conditions are not AEs and should not be reported.

Abnormal laboratory values will not be considered AEs unless:

- the investigator determined that the value is clinically significant,
- the abnormal lab value required intervention, or
- the abnormal lab value required subject withdrawal from the clinical investigation, or
- the abnormal lab value meets the definition of an adverse event.

All adverse events will be collected on each subject throughout the follow up period – until the subject reaches an outcome or withdraws or until the study ends. Causes of death will be captured for all subjects who expire during follow up.

SAE Reporting

The investigator should report all SAEs to the Sponsor as soon as possible but no later than outlined below.

Clinical Investigation Plan

Clinical Site	Reporting timelines
All Sites	SAEs must be reported to the Sponsor no later than 3 calendar days from the day the site personnel became aware of the event or as per the investigative site's local requirements, if the requirement is more stringent than those outlined.

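### SAP 2.10 stops the by-arm adverse event table at one year, so non-fatal events outside the secondary endpoints have no visible category-specific output by arm after month 12

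*SAP*

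**What the plan says.** SAP 2.10 contains one sentence that assigns adverse events to arms, and it carries a time limit: "Adverse events that occur within one year of implant will be reported per randomized treatment group". A later paragraph of the same section sets the format: "Adverse events in the analysis populations will be presented as number and percentage of all subjects enrolled who experience the event", followed by event totals, events per patient-year and a breakdown by severity. That paragraph names neither a window nor the arms.

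The protocol collects for longer. Section 5.8 says: "The expected duration of each subject's participation is at least 12 months and up to 36 months post-implant". Section 2.4.3 continues to supply capsules at month 12 and every six months until closure. Section 6.8.1 says that, for subjects still on capsules, medication details and subject status "along with adverse events and device deficiencies will be collected along with additional supportive data should adverse events or device deficiencies occur". Section 7.3.1 is general: "All adverse events will be collected on each subject throughout the follow up period". Subjects no longer on capsules leave at their month 12 visit (section 5.8).

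**The concern.** The objective is the safety and efficacy of an antiplatelet-free regimen. Myocardial infarction, TIA and venous thromboembolism are defined adverse event categories in Protocol Appendix II. None of them is part of the primary composite or of the major thrombotic rate in SAP 2.3.2, which counts only ischemic stroke, pump thrombosis and arterial peripheral thromboembolism. Myocardial infarction and TIA are arterial ischemic events, where a cost of withdrawing aspirin could plausibly show.

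If SAP 2.10 is followed to the letter, the final report would compare bleeding by arm over the extended blinded period. It would not show how many subjects in each arm had a non-fatal infarction, TIA or venous thromboembolism in that period, although those data will be in the database.

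**Working it through.** **1. Which by-arm outputs reach past month 12**

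| Event | By-arm output after month 12 in the visible text | Place |
|---|---|---|
| Bleeding, including moderate, severe, fatal and GI | Yes; stated to run past one year for some subjects | SAP 2.3.2 |
| Stroke, pump thrombosis | Yes; rates over cumulative exposure, no one-year limit | SAP 2.3.2 |
| Arterial peripheral thromboembolism | Yes; within the major thrombotic rate, no one-year limit | SAP 2.3.2 |
| Death | Yes; Kaplan-Meier and log-rank, and causes by arm | SAP 2.3.2, 2.14 |
| Any event that leads to hospital | Can enter any-cause rehospitalization, but not by diagnosis | SAP 2.3.3 |
| Non-fatal MI, TIA, venous thromboembolism, infection, right heart failure, arrhythmia, hemolysis | None by category | – |

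The Hemocompatibility Score in SAP 2.3.3 has no stated window, and the visible text does not say whether it counts TIA. It is a summary score and not a table by event type.

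**2. The plan's own duration**

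Protocol 5.8: "The expected duration of enrollment is 24 months", and the last subject needs 12 months. 24 + 12 = 36 months, which agrees with "Therefore, the total duration of the clinical investigation is expected to be 36 months". The longest time a subject can spend beyond month 12 is 36 − 12 = 24 months.

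**3. Potential time after month 12**

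Inputs: 628 randomized (Protocol 5.7), 24 months of enrollment (Protocol 5.8), uniform accrual (assumption). Time beyond month 12 is then spread evenly from 0 to 24 months, with mean 24 / 2 = 12 months.

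- After month 12, at most: 628 × 1 year = 628 patient-years.
- Year one, at most: 628 × 1 year = 628 patient-years.

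**4. Time likely to be realized**

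Assumptions not in the documents: 40% to 70% of the potential later time is spent on capsules, and year one yields 90% of its maximum.

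- Year one: 0.9 × 628 = 565 patient-years.
- Low: 0.4 × 628 = 251; share = 251 / (251 + 565) = 31%.
- High: 0.7 × 628 = 440; share = 440 / (440 + 565) = 44%.

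**5. Check under a different model**

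Assume instead a constant hazard of leaving the capsules, with yearly retention r and λ = −ln r. Mean on-capsule time in year one is (1 − r)/λ. Mean on-capsule time after month 12 is (r/λ) × [1 − (1 − r²)/(2λ)], averaged over 0 to 2 years of available time. Multiplying by 628:

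| Assumed yearly retention | Year one (patient-years) | After month 12 (patient-years) | Share after month 12 |
|---|---|---|---|
| 100% | 628 | 628 | 50% |
| 90% | 596 | 528 | 47% |
| 80% | 563 | 435 | 44% |
| 60% | 492 | 276 | 36% |
| 40% | 411 | 148 | 27% |

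The two models agree in order of magnitude. Even at 40% yearly retention, over a quarter of on-capsule time falls after month 12.

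**The case against.** A reader might infer that serious events in the second and third year would be missing from the by-arm report altogether, or that the adverse event table is the only place where a late infarction or embolism could show. The documents do not support either reading. Bleeding, stroke, pump thrombosis, major hemorrhagic and thrombotic events and survival are all compared by arm without a one-year limit. A fatal late event appears under cause of death by arm, and an event that leads to admission can count toward rehospitalization. The gap is confined to non-fatal, category-specific counts.

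Other points on the plan's side:

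- **The format paragraph of SAP 2.10 has no time limit.** True, but it has no by-arm statement either, so the section is at best ambiguous. If full follow-up was meant, a sentence is still needed.
- **A one-year cut is defensible.** Subjects who move to open label are kept to month 12 and normally leave if they move later (Protocol 5.6, 6.8.1). Later data therefore come from a selected on-treatment subset with unequal follow-up. SAP 2.11 counts operative procedures over the same year. This stands as a reason to keep the later table separate and descriptive. It does not justify omitting it, since SAP 2.3.2 already uses such follow-up for bleeding.
- **The patient-years measure exposure, not lost information.** This stands. The same time is analysed for the secondary endpoints, and the documents give no event rates for the categories affected.
- **Redaction.** Protocol section 8, much of SAP 2.1 and parts of the SAP appendices are blacked out, so absence elsewhere cannot be confirmed. SAP 2.10 itself is readable.
- **The DSMB sees unblinded data** (Protocol 10.8.2). That protects subjects during the trial but does not replace the final report.

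**Conclusion.** The point holds in a limited form. The only by-arm adverse event sentence in SAP 2.10 stops at one year, while blinded treatment and adverse event collection can run to month 36. Non-fatal events outside the secondary endpoints have no visible category-specific by-arm output after month 12.

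About 250 to 440 patient-years (31% to 44% of exposure) fall outside this table under the stated assumptions on accrual, later contribution and year-one yield. The constant-hazard check gives 27% to 50%. The retention figures are assumptions, not document figures.

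The primary analysis and the secondary comparisons are unaffected. This is a cheap improvement to safety reporting, not an analysis error.

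**What to change.** Keep the one-year by-arm table in SAP 2.10. Add a separate by-arm table of all adverse events and SAEs from the end of that window to exit or study close. For each category, show subjects with events, number of events and events per patient-year, using only patient-years after month 12 as the denominator. Label it descriptive and state that it covers only subjects still on treatment arm medication. If the sponsor prefers to leave these events out, the SAP should give the reason.

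The cost is a sentence or two in the SAP and one more table from data already collected. The drawback is that the table rests on a selected on-treatment subset and does not support formal comparison between arms.
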